| Treatment-Emergent | Positive                         | 
A post-baseline confirmed positive result exists with a titer <math>\geq 4</math> times greater than the baseline titer
 
OR
 
Any post-baseline confirmed positive result after a negative baseline result
 
Note: The number of treatment-emergent transient positive and treatment-emergent persistent positive ADA will sum to the total positive treatment-emergent ADA
 
Note: If baseline ADA data is missing, the baseline value is treated as negative for this analyses
 | Number of patients with at least one post-baseline ADA assessment |
|                    | Transient Positive iv | 
Scenario 1:
 
(1) Negative ADA at baseline
 
AND
 
(2) Last ADA sampling timepoint is negative
 
AND (3a OR 3b):
 
(3a) Only one post-baseline confirmed positive ADA (excluding the last sampling timepoint) exists and last ADA negative sample is at
   |   |

Sponsor: Boston Pharmaceuticals, Inc.

Protocol Number: BOS161721-02

SAP Version and Date: Version 4.0, 23Apr2021

|  |  |  |  |
|--|--|--|--|
|  |  | 
least 16 weeks apart from the previous confirmed positive sample.
 
OR
 
(3b) Two or more post-baseline confirmed positive ADA where the first and last ADA confirmed positive samples are less than 16 weeks apart (irrespective of any negative ADA in between) and last ADA negative sample is at least 16 weeks apart from the previous confirmed positive sample.
 
Scenario 2:
 
(1) Confirmed positive ADA at baseline
 
AND
 
(2) Last ADA sampling timepoint is negative or is the same as baseline ADA levels
 
AND (3a OR 3b):
 
(3a) Only one post-baseline confirmed positive ADA (excluding the last sampling timepoint) exists and the titer at the post-baseline timepoint is <math>\geq 4</math> times greater than the baseline titer
 
OR
 
(3b) Two or more post-baseline confirmed positive ADA where the first and last ADA confirmed positive samples are less than 16 weeks apart (irrespective of any negative ADA in between) and the titers at each of the two or more post-baseline confirmed positive
 |  |
|--|--|--|--|

Sponsor: Boston Pharmaceuticals, Inc.

Protocol Number: BOS161721-02

SAP Version and Date: Version 4.0, 23Apr2021

|  |                                   |   |  |
|--|-----------------------------------|---|--|

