|  |                                   | 
timepoints are <math>\geq 4</math> times greater than the baseline titer
 
Note: If baseline ADA data is missing, the baseline value is treated as negative for this analyses
   |  |
|  | Persistent Positive iv | 
Scenario 1:
 
(1) Negative ADA at baseline
 
AND (2 OR 3 OR 4):
 
(2) Two or more post-baseline confirmed positive ADA where the first and last ADA confirmed positive samples are more than 16 weeks apart (irrespective of any negative ADA in between)
 
OR
 
(3) Confirmed positive ADA at the last post-baseline assessment
 
OR
 
(4) Negative ADA at the last post-baseline assessment and a prior confirmed positive ADA sample occurred less than 16 weeks before the last post-baseline negative ADA sample
 
Scenario 2:
 
(1) Confirmed positive ADA at baseline
 
AND (2 OR 3 OR 4):
 
(2) Two or more post-baseline confirmed positive ADA where the first and last ADA confirmed positive samples are more than 16 weeks apart (irrespective of any negative ADA in between) and the
 |  |

Sponsor: Boston Pharmaceuticals, Inc.

Protocol Number: BOS161721-02

SAP Version and Date: Version 4.0, 23Apr2021

|                                 |                    |   |   |
|---------------------------------|--------------------|---|---|
|                                 |                    | 
titors at each of the two or more post-baseline confirmed positive timepoints are <math>\geq 4</math> times greater than the baseline titer
 
OR
 
(3) Confirmed positive ADA at the last post-baseline assessment and the titer at the last post-baseline timepoint is <math>\geq 4</math> times greater than the baseline titer
 
OR
 
(4) Negative/similar to baseline ADA at the last post-baseline assessment and a prior confirmed positive ADA sample occurred less than 16 weeks before the last post-baseline negative/similar to baseline ADA sample and the titer of the confirmed positive ADA is <math>\geq 4</math> times greater than the baseline titer
 
Note: If baseline ADA data is missing, the baseline value is treated as negative for this analyses
 |   |
| Post-baseline at each timepoint | Positive           | Confirmed Positive ADA at the post-baseline timepoint   | Number of patients with ADA assessment at baseline and at the post-baseline timepoint |

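### In SAP Table 7, the treatment-emergent transient and persistent ADA classes are not guaranteed to sum to the treatment-emergent total, because the rules for baseline-positive patients both overlap and leave a gap

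*SAP*

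**What the plan says.** All of this is in the SAP (version 4.0), section 8.3, Table 7.

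- **Treatment-emergent positive.** There are two routes. With a positive baseline: "A post-baseline confirmed positive result exists with a titer" at least four times the baseline titre. With a negative baseline: "Any post-baseline confirmed positive result after a negative baseline result". A missing baseline is treated as negative. The note on additivity, that "The number of treatment-emergent transient positive and treatment-emergent persistent positive ADA will sum to the total positive treatment-emergent ADA", stands in the same row.
- **Treatment-emergent transient, Scenario 1 (baseline negative).** The last sample is negative, and "last ADA negative sample is at least 16 weeks apart from the previous confirmed positive sample". With two or more positives, the first and last must also be less than 16 weeks apart.
- **Treatment-emergent transient, Scenario 2 (baseline positive).** Condition 2 is "Last ADA sampling timepoint is negative or is the same as baseline ADA levels". Rule 3a then reads "Only one post-baseline confirmed positive ADA (excluding the last sampling timepoint) exists and the titer at the post-baseline timepoint is" at least four times baseline. Rule 3b requires the first and last positives to be less than 16 weeks apart and applies the fourfold test to "the titers at each of the two or more post-baseline confirmed positive" timepoints. Neither rule sets a minimum interval between the last positive and the final sample.
- **Treatment-emergent persistent, Scenario 2.** Any one of three rules is enough. Rule 2: two or more positives more than 16 weeks apart, each at least fourfold. Rule 3: the last sample is positive and at least fourfold. Rule 4: "Negative/similar to baseline ADA at the last post-baseline assessment and a prior confirmed positive ADA sample occurred less than 16 weeks before" that last sample, with the earlier positive at least fourfold.

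The text above the table says that the treatment-emergent split will be summarized only if the data warrant it. The separate post-baseline transient and persistent split, which ignores baseline status, is planned unconditionally.

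**The concern.** A note that two classes add up to a total is a claim that they are mutually exclusive and exhaustive. In Scenario 1 the pieces fit: at least 16 weeks on the transient side is the complement of less than 16 weeks on the persistent side. In Scenario 2 that matching condition has gone from the transient side only. The fourfold requirement has also moved from any one positive, which makes a patient treatment-emergent, to every positive, which decides the class.

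If a baseline-positive patient has an affected pattern, the programmer finds that the output contradicts the SAP's own note and must choose a rule after seeing the data. Section 2.1 places immunogenicity in the primary objective of the MAD part. The active groups there have 5 or 9 patients (section 3.1.1), so with complete ADA data one patient counted twice or dropped moves a cohort percentage by 1/5 = 20 or 1/9 = 11 percentage points.

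**Working it through.** **Inputs.** The Table 7 rules as summarized above; 16 weeks = 16 × 7 = 112 days. Sampling days 15, 30, 60, 90, 180 and 270 are those that section 8.3 lists for neutralizing antibodies. That ADA is sampled on the same days is an assumption.

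**Overlap, by hand.** Baseline positive; the only positive is at least fourfold, at Day 180; negative at Day 270. The interval is 270 − 180 = 90 days = 12.9 weeks.
- Transient: the last sample is negative, there is a single positive and it is at least fourfold, so rule 3a is met.
- Persistent: a fourfold positive lies 90 < 112 days before the last negative sample, so rule 4 is met.

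The patient is in both classes.

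**Gap, by hand.** Baseline positive; at least fourfold at Day 90, a lower positive at Day 180, negative at Day 270. One fourfold result exists, so the patient is treatment-emergent.
- Transient 3a fails: there are two positives.
- Transient 3b fails: the Day 180 positive is below fourfold.
- Persistent 2 fails: the positives are 180 − 90 = 90 days apart, not more than 112, and one is below fourfold.
- Persistent 3 fails: the last sample is negative.
- Persistent 4 fails: the only fourfold sample is 270 − 90 = 180 days before the last.

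The patient is in neither class.

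**Enumeration.** Every possible sequence over the six days was classified. In Scenario 1 each sample is negative or positive, giving 2^6 − 1 = 63 treatment-emergent patterns. In Scenario 2 each sample is negative, positive below fourfold (taken as the same as or similar to baseline), or positive at least fourfold, giving 3^6 − 2^6 = 665 patterns with at least one fourfold result.

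| Case | Patterns | Transient only | Persistent only | Both | Neither |
|---|---|---|---|---|---|
| Scenario 1, nominal days | 63 | 15 | 48 | 0 | 0 |
| Scenario 1, two samples exactly 112 days apart (Days 15 and 127) | 63 | 23 | 32 | 0 | 8 |
| Scenario 2, last sample left out of the count of positives | 665 | 30 | 401 | 4 | 230 |
| Scenario 2, last sample counted | 665 | 15 | 403 | 2 | 245 |
| Scenario 2, last sample negative | 211 | 15 | 79 | 2 | 115 |

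The third and fourth rows are two readings of the parenthesis in rule 3a about excluding the last sampling timepoint. The last row (3^5 − 2^5 = 211) avoids that question, and also the undefined difference between the same as and similar to baseline. Overlap and gap appear in all three Scenario 2 rows.

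**The 16-week boundary.** The second row arises because the spacing of first and last positives is less than 16 weeks for transient and more than 16 weeks for persistent, so exactly 16 weeks belongs to neither. No pair of nominal days is 112 days apart. Days 60 and 180 are 120 days apart, so actual visit dates 8 days closer would hit the boundary. The Post-Baseline rows of Table 7 use the same rules as Scenario 1 and behave identically.

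**The case against.** The strongest reply concerns scope. Scenario 1 and the post-baseline split, which is the one always reported, partition cleanly on nominal days, and patients with a missing baseline go to Scenario 1. The treatment-emergent split is conditional on the data. The adverse event overview by ADA status uses post-baseline positive and negative, and the optional further adverse event analyses use the post-baseline transient and persistent classes. No test, dose decision or efficacy result is shown to rest on the treatment-emergent split, and by-patient ADA listings would expose a misclassified patient. The number of baseline-positive patients is not given and could be zero. All of this stands, and it sets the size of the point.

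It does not remove the point. The additivity note is a definite statement that the definitions beside it do not support, and the gap pattern, a raised titre that wanes through lower positives to negative, is not contrived.

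A reader might infer more than this: that the two counts cannot add up, that both transient and persistent splits in Table 7 are faulty, or that about a third of baseline-positive patients (230/665) would be lost. The documents do not support these. The counts agree if no baseline-positive patient shows an affected pattern, or if overlaps happen to offset gaps. The post-baseline split is sound apart from the boundary case. The ratio weights all logical patterns equally and says nothing about how often each occurs.

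**Conclusion.** The point holds in limited form. For baseline-positive patients, the treatment-emergent transient and persistent classes are neither mutually exclusive nor exhaustive, so the sum that Table 7 states is not guaranteed. Baseline-negative patients and the post-baseline split are affected only when first and last positives are exactly 16 weeks apart.

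The two worked examples need only the Table 7 rules and samples at Days 90, 180 and 270. The pattern counts rest further on the assumed six-day schedule and the three-level coding of titres. The number of patients affected cannot be estimated from the SAP.

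Section 2.1 names immunogenicity in the MAD primary objective (section 8 calls it secondary for MAD), but it would be wrong to read this as a threat to that objective. What is at risk is one conditional descriptive summary. It is a stated rule that gives the wrong result and is cheap to correct before database lock.

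**What to change.** Reword the treatment-emergent rows of Table 7 so that the sum holds by construction:

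1. Define treatment-emergent persistent first. For baseline-positive patients, judge the spacing of first and last positives, and the interval to the last sample, only on samples at least four times the baseline titre. Set the first-to-last spacing at 16 weeks or more.
2. Define treatment-emergent transient as every other treatment-emergent positive patient.
3. Use the same boundary of 16 weeks or more for persistent in Scenario 1 and in the Post-Baseline rows, so that exactly 16 weeks belongs to one class.
4. Use one term, with a stated titre limit, for a last sample that has returned to baseline level, in place of the two now used.

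The additivity note can then stay as it is. The cost is a rewording of Table 7 and minor programming; no new data are needed.

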### 8.3. Immunogenicity

Immunogenicity data as collected on the eCRF will be provided in by-patient data listings including neutralizing antibodies (NAb) and ADA for all relevant timepoints.

All serum ADA samples that are confirmed positive in the ADA assay will be analyzed for the presence of NAb.

The proportion of patients with positive or negative ADA will be summarized by study phase, treatment group, and overall, at baseline (pre-dose), and post-baseline in the FAS. The frequency and percentage of patients with transient positive and persistent positive ADA will also be included in the summary. If warranted based on data, treatment-emergent transient positive and treatment-emergent persistent positive ADA will be summarized. The frequency and percentage of patients with confirmed positive, treatment-emergent confirmed positive, and negative ADA at each post-baseline timepoint will also be summarized. ADA designations and denominators are defined in table 7.

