**Table 7**

| Timepoint                 | ADA Designations | Definition                         | Denominator/Evaluable Patients                      |
|---------------------------|------------------|------------------------------------|---|
| Baseline (Day 0 Pre-Dose) | Positive         | Confirmed positive ADA at baseline | Number of patients with a baseline and at least one |

Sponsor: Boston Pharmaceuticals, Inc.  
 Protocol Number: BOS161721-02  
 SAP Version and Date: Version 4.0, 23Apr2021

|               |                                   |  |   |
|---------------|-----------------------------------|--|---|
|               | Negative                          | Negative ADA at baseline   | post-baseline ADA assessment                                      |
| Post-Baseline | Positive                          | Confirmed positive ADA at any time after baseline  | Number of patients with at least one post-baseline ADA assessment |
|               | Negative                          | Negative ADA at all times after baseline   |   |
|               | Transient Positive iv  | 
(1) Last ADA sampling timepoint is negative
 
AND 2a OR 2b:
 
(2a) Only one post-baseline confirmed positive ADA (excluding the last sampling timepoint) exists and last ADA negative sample is at least 16 weeks apart from the previous confirmed positive sample.
 
OR
 
(2b) Two or more post-baseline confirmed positive ADA where the first and last ADA confirmed positive samples are less than 16 weeks apart (irrespective of any negative ADA in between) and last ADA negative sample is at least 16 weeks apart from the previous confirmed positive sample.
 |   |
|               | Persistent Positive iv | 
1 OR 2 OR 3:
 
(1) Two or more post-baseline confirmed positive ADA where the first and last ADA confirmed positive samples are more than 16 weeks apart (irrespective of any negative ADA in between)
 
OR
   |   |

|                    |                                  |  |   |
|--------------------|----------------------------------|--|---|
|                    |                                  | 
(2) Confirmed positive ADA at the last post-baseline assessment
 
OR
 
(3) Negative ADA at the last post-baseline assessment and a prior confirmed positive ADA sample occurred less than 16 weeks before the last post-baseline negative ADA sample
  |   |

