|                                 | Treatment-Emergent | 
Scenario 1:
 
(1) Negative ADA at baseline
 
(2) Confirmed positive ADA at the post-baseline timepoint
 
Scenario 2:
 
(1) Confirmed positive ADA at baseline
  |   |

|         |          |  |  |
|---------|----------|--|--|
|         |          | (2) Confirmed positive ADA at the post-baseline timepoint and the titer at the of the confirmed positive ADA is $\geq 4$ times greater than the baseline titer |  |
|         | Negative | Negative ADA at the post-baseline timepoint  |  |
| Overall | Positive | A patient with positive baseline (pre-dose) ADA or positive post-baseline ADA  | Number of patients with a baseline or post-baseline ADA assessment |
|         | Negative | A patient with negative baseline (pre-dose) ADA and negative post-baseline ADA at all time points  |  |

The frequency and percentages of positive and negative neutralizing antibodies will be summarized in the FAS overall and at each relevant post-baseline timepoint (i.e., Day 15, Day 30, Day 60, Day 90, Day 180, Day 270). The denominators will be the number of patients with non-missing NAb data overall and at each timepoint, respectively.

The adverse event overview table from section 10.1 will be repeated by post-baseline positive and negative ADA as defined in table 7 in the safety analysis set. Additional adverse event analyses may be performed by post-baseline transient positive and persistent positive.

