### 10.1. Adverse Events

AEs will be collected and recorded for each patient from the date of the first dose of study drug until the end of their participation in the study, including the safety follow up period. Severity of adverse events will be graded by the investigator according to National Cancer Institute Common Terminology Criteria for Adverse Events (NCI CTCAE) version 4.03. AEs will also be assessed for relationship to study drug, and seriousness. Adverse events will be marked as AESIs, dose-limiting toxicities (DLTs), or injection site reactions (ISRs), where applicable. AEs will be considered treatment-emergent adverse events (TEAEs) if they started any time after first dose or if the year, month and day of start date were missing. Any missing severity assessments will be assumed to be Grade 3, missing relationship assessments will be assumed to be related, and missing seriousness assessments will be assumed as serious.

An overview of TEAEs will be produced, including counts and percentages of patients with any incidences of TEAE, TEAEs related to study treatment, SAEs, SAEs related to study treatment, any CTCAE grade 2 or higher TEAEs, any CTCAE grade 2 or higher TEAEs related to study treatment, any CTCAE grade 3 TEAEs, any CTCAE grade 3 or higher TEAEs related to study treatment, any CTCAE grade 4 TEAEs, any CTCAE grade 4 or higher TEAEs related to study treatment, TEAEs leading to study treatment discontinuation, treatment related TEAEs leading to study treatment discontinuation, TEAEs of special interest, related TEAEs of special interest, DLTs, related DLTs, TEAEs resulting in death, related TEAEs resulting in death, and injection site reactions. The maximum CTCAE grade (Grades 1-5) will also be included on the summary table.

Adverse events will be coded based on the MedDRA. Patients will be counted once per SOC (and likewise for PT within SOC). TEAEs will be summarized by SOC and PT in descending order of overall incidence of SOC (and PT within SOC). The MedDRA version used is defined in the study data management plan.

Summaries of adverse events by SOC and PT will include the following types:

- TEAEs;
- TEAEs related to study treatment;
- SAEs;
- Related Serious TEAEs;
- CTCAE Grade 3 or higher TEAEs;
- CTCAE Grade 3 or higher TEAEs related to study treatment;
- TEAEs leading to treatment discontinuation; and
- Dose-Limiting Toxicities
- TEAEs of Special Interest

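### The one committed AE-by-ADA table groups patients by any positive sample after baseline, so unchanged pre-existing antibody counts as positive and events before detection are pooled with later ones

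*SAP*

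**What the plan says.** All references are to the SAP, Version 4.0.

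- **Committed display (Section 8.3, after Table 7):** "The adverse event overview table from section 10.1 will be repeated by post-baseline positive and negative ADA as defined in table 7". The safety population is used for this table.
- **Optional display (same place):** "Additional adverse event analyses may be performed by post-baseline transient positive and persistent positive". This uses the post-baseline transient and persistent classes, not their treatment-emergent counterparts.
- **Post-baseline positive (Table 7):** "Confirmed positive ADA at any time after baseline", with no condition on baseline status or titer. The negative group is negative throughout.
- **Treatment-emergent positive (Table 7):** either a titer at least 4 times the baseline titer, or "Any post-baseline confirmed positive result after a negative baseline result". A missing baseline is treated as negative.
- **Event window (Section 10.1):** "AEs will be considered treatment-emergent adverse events (TEAEs) if they started any time after first dose". The overview reports results "including counts and percentages of patients with any incidences of TEAE" and similar patient-level counts, with no onset timing.
- **Other ADA output (Section 8.3):** "The frequency and percentage of patients with confirmed positive, treatment-emergent confirmed positive, and negative ADA at each post-baseline timepoint will also be summarized". Listings are also promised: "Immunogenicity data as collected on the eCRF will be provided in by-patient data listings including neutralizing antibodies (NAb) and ADA for all relevant timepoints". The comprehensive AE listing in Section 10.1 is a separate output.

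**The concern.** The purpose of an AE-by-ADA table is to show whether patients who develop antibody to the drug have a different safety profile. Two features of the planned grouping blur that picture.

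First, antibody that was present before dosing and did not rise was not induced by the drug. Table 7 recognises this by defining a treatment-emergent class in detail, and the SAP tabulates that class as an incidence. No AE analysis, committed or optional, uses it.

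Second, an event that began before the first positive sample is credited to the positive column exactly like one that began afterwards. Neither Section 8.3 nor Section 10.1 relates event onset to the date of detection.

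What is at stake is the readability of one safety display. ADAs are a listed safety endpoint in both phases (Sections 2.1 and 2.2), and immunogenicity is part of the Phase 1b primary objective in Section 2.1, although the opening of Section 8 calls it secondary in Phase 1b and exploratory in Phase 2.

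**Working it through.** The SAP states no ADA rate, baseline-positive rate or time to seroconversion, so there is no figure of its own to reproduce. The definitions settle whether the point exists; its size can only be illustrated.

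**Step 1. Definitions side by side.** Take a patient who is confirmed positive at Day 0 and at the same titer at Day 90. Post-baseline positive: yes. Treatment-emergent positive: no, because the baseline was not negative and the titer is below 4 times baseline. The AE table places this patient in the positive column. A patient with a missing baseline is treated as negative, so any later positive is treatment-emergent; such patients do not add to the mismatch.

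**Step 2. How much of the positive column could be unchanged antibody.** Let *b* be the baseline-positive prevalence (assuming these patients stay positive) and *t* the probability of treatment-emergent ADA. The share of the ever-positive group that is not treatment-emergent is b(1−t) / [b + (1−b)t]. All values are assumed.

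| b | t = 5% | t = 10% | t = 20% |
|---|---|---|---|
| 0% | 0% | 0% | 0% |
| 2% | 28% | 15% | 7% |
| 5% | 49% | 31% | 17% |
| 10% | 66% | 47% | 29% |

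For example, at b = 5% and t = 10%: 0.05 × 0.90 / (0.05 + 0.95 × 0.10) = 0.045 / 0.145 = 31%. At b = 0 the two groupings are identical.

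**Step 3. Effect on the table's own metric.** A simulation let treatment-emergent antibody truly double the AE rate, with ADA incidence 10–30% and unchanged pre-existing antibody in 0, 2, 5 or 10% of patients. The percentage with any TEAE in the ever-positive column came out below that in the treatment-emergent group by 0, 0.8–3.7, 1.9–7.3 or 3.5–11.0 points. The standard error of the positive-minus-negative gap, among 73 active Phase 2 patients, was 11–22 points.

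**Step 4. Events before detection.** Follow-up runs to Day 270 (Section 3.1). For a first positive sample on day *d*, the fraction of follow-up before detection is d/270: 15/270 = 6%, 30/270 = 11%, 60/270 = 22%, 90/270 = 33%, 180/270 = 67%, 270/270 = 100%. These are the days that Section 8.3 lists for neutralizing antibody.

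**Step 5. Share of first AEs that precede detection.** A simulation assumed no true link between antibody and AEs, and independent AE and dropout times. AE incidence was 30–70%, ADA 2–30% and dropout 10–30%. Sampling was on the neutralizing-antibody days or on Day 15 and then monthly. Among ADA-positive patients with an AE, the share whose first AE came before the first positive sample was:

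| Assumed seroconversion timing | Share |
|---|---|
| Constant hazard to Day 270 | 55–69% |
| Uniform over first 90 days | 24–34% |
| Uniform over first 60 days | 18–26% |
| Uniform over first 30 days | about 10–15% |

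The onset pattern drives the result more than the other inputs together, and the SAP is silent on it. The range is therefore about 10–69%.

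**Step 6. Numbers available.** Active Phase 2 patients: 110 × 2/3 ≈ 73. At 10% ADA incidence, 73 × 0.10 = 7.3 before losses; about 6–7 would be detected on study. Phase 1b has 5 + 9 + 9 = 23 active patients, so about 2.

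**The case against.** The strongest reply is that the SAP contradicts nothing here. It names one grouping, defines it and applies it consistently. An ever-positive group is a defensible inclusive choice for a descriptive table because it loses no patient with detected antibody. That stands, and is why the planned table should be kept.

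Several further points also stand. The grouping part vanishes without unchanged pre-existing antibody, and in most illustrated cases the shift is well inside sampling error. Section 3.1.2 reports no immunogenicity trend at the interim analysis. Section 10 splits safety output by phase and treatment group, so antibody-positive placebo patients give some context. With few positives, a reader can match the ADA and AE listings by hand. Listing layouts belong to the mock shells (Section 13.12), which are not shown and might already carry the ADA date.

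A reader might infer from the timing issue that most events in the positive column precede antibody, or that a before/after table is needed. The documents support neither. A figure above one half requires seroconversion spread evenly over nine months; with early onset the share falls to about 10%. A before/after table would have very few patients on each side, and the split is confounded with time since first dose.

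The reply does not explain why a class the SAP defines carefully, and counts at each visit, is used in no AE analysis.

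**Conclusion.** The point holds as a modest improvement to a descriptive display. By the SAP's own definitions, the only committed AE-by-ADA table mixes unchanged pre-existing antibody with drug-induced antibody, and pools events from before and after detection.

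The size is unknown. The grouping effect runs from nothing upward with the unstated baseline-positive rate, and the timing effect is about 10–69% under assumed rates and onset patterns. Confidence in the definitional reading is high; confidence in the magnitude is low.

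It would go too far to infer that the table would give a wrong safety conclusion, or that ADA incidence or efficacy results are affected. The table is untested, the incidence summaries use the treatment-emergent class separately, and no efficacy analysis depends on this grouping. The change is worth making because it is cheap, not because the plan fails without it.

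**What to change.** Keep the planned table and add to Section 8.3:

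> The AE overview will also be repeated by Table 7 treatment-emergent ADA (positive versus not positive, among patients with at least one post-baseline ADA assessment), and for treatment-emergent positive patients the date of the first treatment-emergent positive sample will be included in the AE listing.

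The regrouped table removes unchanged pre-existing antibody from the positive column. The date lets a reader judge timing case by case, so no before/after table is needed.

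The cost is one SAP sentence, one repeated table and one listing column, all from data already collected. The drawback is sparse output: about 6–7 treatment-emergent positives of 73 active Phase 2 patients at 10% ADA incidence, and at 2% only one or two (73 × 0.02 ≈ 1.5 before losses), where the listing date would be the useful part.
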